11.1.1.2 EU Regulatory Submission

The primary efficacy endpoint for Ex-U.S. submission is defined as the hemoglobin change from baseline to the average hemoglobin of Weeks 28 to 36, without having received rescue therapy within 6 weeks prior to and during this 8-week evaluation period and will be based on the PPS population based on patients enrolled during the original protocol before the amendment 1. This primary efficacy analysis will be based on the estimated difference between the two treatments overall mean effects throughout the evaluation period based on the MMRM model described below.

The primary hypothesis to be tested for the primary efficacy analysis for Ex-US submission is:

H_0 : Hemoglobin mean change from baseline to the average of week 28 to week 36 in the Roxadustat group
 \leq Hemoglobin mean change from baseline in the Epoetin alfa group minus 0.75 g/dL

Versus

H_1 : Hemoglobin change from baseline to the average of week 28 to week 36 in the roxadustat group
 $>$ Hemoglobin mean change from baseline in the Epoetin alfa group minus 0.75 g/dL

Rescue therapy for all subjects is defined as ESA rescue or RBC transfusion. For subjects who require rescue therapy, the hemoglobin value after the initiation of the rescue therapy will be set to missing up to 6 weeks (or 8 weeks if during the evaluation period) from the last date of the rescue therapy.

The primary endpoint for EU Regulatory. will be analyzed using MMRM using baseline value as covariate and treatment group, visit (up to Week 52), interaction of treatment group

and visit, and stratification factors except mean qualifying screening hemoglobin (≤ 10.5 vs. >10.5 g/dL) as fixed effects.

Due to the large amount of visits (up to Week 52) to be included in the model, the unstructured covariance pattern model will be applied first. If the algorithm for unstructured covariance pattern does not converge then the heterogeneous Toeplitz structure will be used. If this second model does not converge either then the (homogeneous) Toeplitz structure will be tried and finally compound symmetry as a covariance structure to achieve convergence.

The estimates for difference of change in Hb averaged over Weeks 28 to 36 between the two treatment groups will be generated from an estimate statement from Visit Week 28 to 36.

This null hypothesis will be rejected if the two-sided 95% confidence interval for the difference of least square means between the two treatment groups using the MMRM model lies entirely above -0.75 g/dL.

11.1.2 Sensitivity Analyses of Primary Endpoint

The potential impact of missing data on the estimates of the primary efficacy endpoint will be examined using the following sensitivity analyses. The results of the analyses will be summarized in Table 5. These sensitivity analyses are further detailed in each Section.

Table 5: Primary Endpoint Analysis Results

Analysis (ITT for U.S. and PPS Ex-U.S.)	Treatment Difference and 95% CI (roxadustat vs Epo)	Std. Err.	Degree of Freedom*	t-statistics	p-value
ANCOVA with Multiple Imputations	.xxx (.xxx, .xxx)	.xxx	xxx	.xxx	.xxxx
ANCOVA-MI with Hb censored** for rescue therapy (US endpoint only)	.xxx (.xxx, .xxx)	.xxx	xxx	.xxx	.xxxx
MMRM	.xxx (.xxx, .xxx)	.xxx	xxx	.xxx	.xxxx
PMM-Last Mean Carried Forward	.xxx (.xxx, .xxx)	.xxx	xxx	.xxx	.xxxx
ANCOVA-MI for subjects enrolled in original protocol	.xxx (.xxx, .xxx)	.xxx	xxx	.xxx	.xxxx

* Maximum of Degree of Freedom from each individual ANCOVA. The actual Degrees of Freedom in PMM will be calculated using

$$df = (m - 1) \left(1 + \frac{m \bar{U}}{(m + 1)B} \right)^2$$

where B is

$$\bar{U} = \frac{1}{m} \sum_{j=1}^m U_j$$

between-imputation variance and

with U the standard error associated with estimates, Rubin (1987).

**Rescue therapy for all subjects is defined as ESA rescue or RBC transfusion. For subjects who require rescue therapy, the hemoglobin value after the initiation of the rescue therapy will be set to missing up to 6 weeks (or 8 weeks if during the evaluation period) from the last date of the rescue therapy.

11.1.2.1 MMRM

The same analysis as Ex-U.S. primary endpoint will be repeated for the primary U.S. endpoint as one of the sensitivity analysis.

11.1.2.2 Pattern Mixture Model

PMMs provide a general and flexible framework for sensitivity analyses that allows formulating assumptions regarding missing data in a transparent and clinically interpretable manner. This is expected to address the possibility of the data being missing not at random (MNAR). All factors mentioned in the primary analysis will be included in the PMM.

The following aspects of data missingness, may affect the estimates.

- Timing and extent of missingness
- Assumed underlying mechanism for data missingness

11.1.2.2.1 Timing and Extent of Missing Data

To assess the potential effect of data missingness on the estimate of treatment effect, subjects will be classified as full data or missing data cases. Patterns of missingness will be based on non-missing hemoglobin before the end of the evaluation period.

- Full data cases are defined as subjects with non-missing hemoglobin for all scheduled weeks of the Treatment period.
- Missing data cases are defined as subjects with a missing hemoglobin on at least one scheduled Week of the treatment period. The missing data cases are further grouped into intermittent missing and monotone missing cases.
 - Intermittent missing hemoglobin cases are defined as subjects with a missing hemoglobin for at least one scheduled week of but not on consecutive scheduled weeks up to end of the evaluation period.
 - Monotone missing hemoglobin cases are defined as subjects who have consecutive scheduled Weeks with missing hemoglobin up to the end of evaluation period. A subject who is a Monotone missing case could have intermittent missing hemoglobin prior to the ending Week.

Subjects will be grouped as follows:

- Full data cases
- Intermittent missing data cases
- Monotone missing data cases

Should the incidence of Monotone missing data cases and intermittent missing data cases be relatively small, 5%, then those cases will be combined so that the groups are full data

cases and missing data cases. The summary of missing pattern in first 52 scheduled visits will be presented in a table.

11.1.2.2.2 Assumptions on Missing Data Mechanism

In addition to the extent of data missingness, the mechanism under which missing data occur may affect the estimate of the parameter of interest.

The potential impact of missing efficacy endpoints on the estimates of treatment effects will be assessed using alternative statistical models with different underlying assumptions on the missing data mechanism (missing not at random (MNAR)) (Little and Rubin, 1987).

11.1.2.2.3 PMM –Last Mean Carried Forward

A pattern-mixture model using a last mean carried forward multiple imputation method (Carpenter et al, 2013) will be used as another sensitivity analysis to explore the robustness of the ANCOVA results for the primary efficacy variables. Using this method, missing data after ending Week will be imputed based on the last non-missing mean from its own treatment group.

The steps to implement this sensitivity analysis are as follows. Parameters below refer to the parameters of the multivariate normal distribution for baseline and post baseline Hb measurement.

1. Create posterior distribution of parameters: Separately for each treatment arm, take all patients observed data and assuming MAR to fit a multivariate normal distribution with unstructured mean (i.e. a separate mean for each of the baseline plus post-baseline scheduled weeks and unstructured variance covariance matrix using a Bayesian approach with an improper prior for the mean and an uninformative Jeffreys' prior for the variance-covariance matrix (Schafer, 1997, p. 155).
2. Draw parameters: Separately for each treatment arm, draw variance-covariance matrix from the posterior distribution for the parameters using seed 453628 for U.S. and 386045 for Ex-U.S. The mean Vector would be set to the marginal mean for their randomized treatment arm at their last non-missing measurement.
3. Build joint distribution of missing data and observed data: For each subject with missing data, using the draws for the parameter to build the joint distribution of their observed and missing data.
4. Construct conditional distribution of missing data give observed data: For each patient with missing data, use their joint distribution in previous step to construct their conditional distribution of missing given observed outcome data. Sample their missing data from this conditional distribution, to create a 'completed' data set, using seed 732545 for U.S. and 538529 for Ex U.S.

Repeat the above steps for 200 times and resulting in 200 imputed data sets. Then fit ANCOVA model for each imputation data set, and combine the resulting parameter estimates and standard errors using Rubin's rules (Rubin, 1987) for final inference. This sensitivity analysis will be performed for both U.S. and Ex-U.S. primary endpoints.

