#### **4.1.4 Long-term Follow-Up for Premature Treatment Discontinued Subjects**

Subjects who discontinue study medication prematurely will be followed up for vital status, CV events, and hospitalization until study closure, unless consent to participate is withdrawn. Upon completion of EOT and EOS visits, these subjects will be followed up every 3 to 6 month interval (depending on the availability of subjects) until study closure. These visits may occur either in-person or via telephone.

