5 GENERAL STATISTICAL CONSIDERATIONS

5.1 Sample Size Determination

At least 600 subjects and up to 1200 subjects will be randomized via IXRS to receive roxadustat or epoetin alfa in a 1:1 ratio. Study drug will be administered in an open-label manner. Randomization will be stratified by the following four factors:

- Mean qualifying screening hemoglobin (≤ 10.5 vs. >10.5 g/dL)
- History of cardiovascular, cerebrovascular or thromboembolic diseases (Yes vs. No)
- Mean prescribed baseline epoetin alfa dose (or, equivalent epoetin dose for non-epoetin subjects) in 4 weeks prior to randomization (≤ 150 vs. >150 IU/kg/week)

Up to 600 subjects will be enrolled in this study in each treatment group. During the course of this study, which is being conducted in parallel with other Phase 3 studies, up to 1200 subjects may be enrolled for safety evaluation of roxadustat in comparison to epoetin alfa including pre-specified and adjudicated safety events of interest (i.e., all-cause death, MI, stroke, congestive heart failure requiring hospitalization, unstable angina requiring hospitalization, DVT, pulmonary embolism, vascular access thrombosis, and hypertensive emergency). The final number of patients to be enrolled will be based on the enrollment rate of other studies within the same indication, in order to optimize stopping these studies at comparable time frame.

With at least 600 subjects, the study will provide at least 99% power to demonstrate statistical non-inferiority of roxadustat versus ESA in the primary endpoint for US (FDA) submission (i.e., specifically, hemoglobin change from baseline to the average level during the evaluation period defined as Week 28 until Week 52).

The study will provide at least 99% power to demonstrate statistical non-inferiority of roxadustat versus ESA in the primary endpoint outside of the United States (i.e., specifically, hemoglobin change from baseline in the averaged hemoglobin over Weeks 28 to 36). This assumes a difference (roxadustat minus ESA) of -0.30 g/dL, a non-inferiority margin for this difference of 0.75 g/dL and a standard deviation of 1.25 g/dL. Appendix 7 has description on the justification that the non-inferiority margin of 0.75 was used.

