11.1 Analyses of Primary Endpoint

11.1.1 Primary Endpoint and Hypothesis

11.1.1.1 U.S. Submission

The primary efficacy endpoint for the US (FDA) submission is defined as the hemoglobin change from baseline to the average level during the evaluation period defined as Week 28 until Week 52.

The primary hypothesis to be tested for the primary efficacy analysis for US (FDA) submission is:

H_0 : Hemoglobin mean change from baseline to the average level from Week 28 to Week 52 in the roxadustat group \leq hemoglobin mean change from baseline in the epoetin alfa group minus 0.75 g/dL

Versus:

H_1 : Hemoglobin change from baseline to the average level of Week 28 to Week 52 in the roxadustat group $>$ hemoglobin mean change from baseline in the epoetin alfa group minus 0.75 g/dL

A Multiple Imputation (MI) analysis of covariance (ANCOVA) model will be used. The model will contain terms for treatment group, baseline Hb measurement, and stratification factors except mean qualifying screening hemoglobin (≤ 10.5 vs. >10.5 g/dL). The primary efficacy analysis will be based on the estimated difference between the two treatments overall mean effects throughout the evaluation period based on the pooled ANCOVA model.

This null hypothesis will be rejected if the two-sided 95% CI for the difference between the two treatment groups using MI ANCOVA model lies entirely above -0.75 g/dL. Hemoglobin values under the influence of a rescue therapy will not be censored in this analysis.

The below stratification factors will be used in efficacy analyses.

- Mean qualifying screening hemoglobin (≤ 10.5 vs. >10.5 g/dL) for other than Hb related endpoints
- History of CV, cerebrovascular, or thromboembolic diseases (yes vs. no)
- Mean prescribed weekly epoetin alfa dose (or, equivalent epoetin dose for nonepoetin subjects) in the 4 weeks prior to randomization (≤ 150 vs. > 150 IU/kg/week)
- Incident dialysis within ≤ 4 months vs. > 4 months of starting dialysis when randomized.

The following steps will be used to conduct the primary analysis of the primary endpoints for both regions:

1. Generate 200 datasets, using seed 162345 for U.S. and 347631 for Ex-U.S., where only intermittent missing hemoglobin data will be imputed for each treatment relying on non-missing data from all subjects within each treatment group using the Monte Carlo Markov Chain, MCMC) imputation model and the available non missing hemoglobin for each scheduled Week by treatment group.

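### The only pattern-mixture analysis carries the own-arm mean forward without a penalty, so no planned missing-data analysis shows how much lower unobserved roxadustat Hb must be to lose non-inferiority

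*SAP*

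**What the plan says.** **US primary analysis (SAP 11.1.1.1).** The decision rule reads: "This null hypothesis will be rejected if the two-sided 95% CI for the difference between the two treatment groups using MI ANCOVA model" lies wholly above -0.75 g/dL. There are 200 imputed datasets. In step 1, intermittent gaps are "imputed for each treatment relying on non-missing data from all subjects within each treatment group". In step 2, the missing tail up to the end of the evaluation period is filled week by week, separately by arm, by regression on earlier Hb. Both steps assume data missing at random (MAR).

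**Sensitivity analyses (SAP 11.1.2, Table 5).** Besides the primary model, the rows are multiple-imputation ANCOVA with Hb censored for rescue (US only), MMRM, last mean carried forward, and original-protocol subjects only. Of pattern-mixture models, 11.1.2.2 says: "This is expected to address the possibility of the data being missing not at random (MNAR"). Section 11.1.2.2.2 promises alternative models under that mechanism (MNAR). The only one then specified is 11.1.2.2.3, where "missing data after ending Week will be imputed based on the last non-missing mean from its own treatment group". It fits each arm separately under MAR and sets the mean to the arm's mean at the subject's last observed visit. It then draws the missing values conditional on what that subject contributed. No delta adjustment or tipping point appears.

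**Follow-up (Protocol 4.1.4).** "Subjects who discontinue study medication prematurely will be followed up for vital status, CV events, and hospitalization until study closure". Hb is drawn at the EOT visit and at the EOS visit four weeks later (Protocol 7.1.2.5, 7.2.1). None is scheduled after that.

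**The concern.** A randomized subject who stops study drug well before Week 28 will normally have no scheduled Hb in Weeks 28 to 52, so the ITT estimate depends on imputation for that subject.

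The departure that threatens non-inferiority is that roxadustat subjects who stopped would have had lower Hb than imputed. The protocol makes this plausible. Lack of efficacy is a listed reason for stopping (5.3). A roxadustat subject who needs more than one cycle of ESA rescue must stop permanently, whereas an epoetin subject may be switched to another EPO analogue with no matching stop rule (4.6.3.2).

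The primary analysis and the MMRM assume MAR. If the one analysis labelled as MNAR gives nearly the same answer by construction, agreement among the three says little about this departure. A report could then describe the result as robust to informative dropout without having tested it.

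**Working it through.** **Inputs**
- SAP 5.1: "This assumes a difference (roxadustat minus ESA) of -0.30 g/dL" and "a non-inferiority margin for this difference of 0.75 g/dL and a standard deviation of 1.25 g/dL". The protocol synopsis also has -0.30; Protocol 9.1 prints 0.30 without the sign. I use -0.30.
- SAP 5.1: 600 to 1200 subjects randomized 1:1, so 300 to 600 per arm.
- Missing fraction *f* in the roxadustat arm: not in the documents. Assumed range 10% to 40%.

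**1. Reproduce the plan's figure.** SAP 5.1: "With at least 600 subjects, the study will provide at least 99% power to demonstrate statistical non-inferiority of roxadustat versus ESA". SE = 1.25 × √(2/300) = 0.102. Power = Φ((0.75 - 0.30)/0.102 - 1.96) = 99.28%. The stated power reproduces.

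**2. Headroom.** If the observed difference equals -0.30:
- 300 per arm: lower bound = -0.30 - 1.96 × 0.102 = -0.50; headroom to -0.75 is 0.25 g/dL.
- 600 per arm: SE = 1.25 × √(2/600) = 0.072; lower bound = -0.441; headroom 0.309 g/dL.

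**3. Tipping shift.** If each missing subject lacks all of Weeks 28 to 52, lowering the imputed roxadustat values by δ moves the arm mean by *f* × δ. With SE held fixed, the tipping δ is headroom / *f*:

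| Assumed *f* | 300/arm, difference -0.30 | 600/arm, difference -0.30 | 300/arm, difference 0 |
|---|---|---|---|
| 10% | 2.50 | 3.09 | 5.50 |
| 20% | 1.25 | 1.54 | 2.75 |
| 30% | 0.83 | 1.03 | 1.83 |
| 40% | 0.62 | 0.77 | 1.37 |

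All shifts are in g/dL. In the last column the lower bound is -0.20 and the headroom 0.55.

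**4. What the last-mean model adds to MAR.** Within an arm, its estimate differs from the MAR estimate by *f* × (arm mean at the last observed visit - arm mean over Weeks 28 to 52). With a flat arm mean this is zero, whatever happened to Hb after dropout.

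**5. Simulation check.** 60,000 subjects per arm, 30% of roxadustat and 20% of epoetin missing, last observed visit between Weeks 6 and 24. These fractions and the correlation structure are assumptions.

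| Scenario (roxadustat minus epoetin) | Truth | MAR | Last mean |
|---|---|---|---|
| Flat means, dropouts MAR | -0.30 | -0.30 | -0.30 |
| Flat means, roxadustat dropouts 1.0 g/dL worse afterwards | -0.60 | -0.30 | -0.30 |
| Flat means, roxadustat dropouts 2.0 g/dL worse afterwards | -0.89 | -0.30 | -0.30 |
| Roxadustat 0.8 below epoetin in Weeks 6-24, then at -0.30 | -0.30 | -0.30 | -0.45 |

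In the third row the true difference lies beyond the margin and neither method registers it. In the fourth the last-mean model does move, by 0.30 × (-0.80 + 0.30) = -0.15, but in response to the arm's time trend and not to anything that happened after dropout.

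**The case against.** Several points on the other side stand, and they limit the claim.

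- **A reader might infer that no planned sensitivity analysis could challenge non-inferiority.** The documents do not support that. The last-mean model moves when arm means trend over time, and trends are plausible: roxadustat starts from a converted dose, is normally constant for four weeks, then is titrated toward about 11 g/dL. The rescue-censored, MMRM and original-protocol rows, the amended-protocol ITT analysis and the EU repeat on the FAS (Protocol 9.4.3.1) could each give a different answer. None is a penalised MNAR analysis.
- **A reader might infer that own-arm imputation is itself the fault.** For non-inferiority, borrowing from the control arm would be weaker, because it shrinks a difference *d* to (1 - *f*) × *d*. At *f* = 30% a true -0.75 becomes -0.525, and with SE 0.102 non-inferiority would be declared falsely about 60% of the time. What is missing is the penalty.
- **Decline already observed is partly carried.** Step 2 and the last-mean model both condition on the subject's earlier Hb, and an early-termination value is mapped to a scheduled visit if the subject has been off drug no more than 7 days (SAP Appendix 5). Only deterioration beyond that history goes untested.
- **The direction is plausible, not established.** ESA may be resumed after discontinuation, the US primary does not censor Hb under rescue, and some missing data may be administrative because treatment may be shortened for Amendment 1 and 2 subjects.
- **Dropouts before Week 28 count as non-responders** in the first secondary endpoint (SAP 11.2.2.1). That applies to both arms and leaves the primary endpoint untouched.

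**Conclusion.** The point holds as a gap between the SAP's stated purpose and its method. The single pattern-mixture model is offered as the MNAR analysis, but it adds no penalty and is nearly a repeat of MAR when arm means are stable. No planned missing-data analysis reports how much worse unobserved roxadustat Hb must be to lose non-inferiority.

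The size cannot be fixed from the documents. The column for 300 per arm and -0.30 takes the minimum sample size, an observed difference equal to the planning value, a fixed SE and total absence from the evaluation period. The last of these overstates the effect for later dropouts, whose observed values stay in the average. A reader might infer that the result would be fragile; the documents do not support that either. At 10% missing the required shift is 2.5 g/dL, whereas at 40% it is 0.62 g/dL, less than the margin itself. Which case applies is what the analysis should report. This is a cheap improvement worth making and does not invalidate the primary analysis.

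**What to change.** Keep the last-mean model and add a delta-adjusted tipping-point analysis to SAP 11.1.2 and Table 5 for the US primary endpoint:

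- Use the existing 200 completed datasets.
- Subtract δ only from roxadustat values imputed in step 2 (monotone missing after discontinuation). Leave intermittent gaps filled in step 1 and all epoetin values unchanged.
- Increase δ from 0 in 0.15 g/dL steps. At each step refit the ANCOVA and pool by Rubin's rules.
- Continue until the pooled 95% lower bound crosses -0.75. A grid ending at 0.75 would miss the crossing in the illustration at 30% missing or less with 300 per arm and -0.30.
- Report the tipping δ with the missing fraction in each arm, so a reader can judge whether a shift of that size is credible.

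The cost is one shift applied to datasets already generated and one extra table. The downside for the sponsor is that it may show a fragile result.

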11.1.3 Subgroup Analyses

The analysis of the primary endpoints of US and Ex-US may be performed by gender, age group, baseline hemoglobin categories, mean prescribed weekly epoetin alfa dose categories, baseline CRP categories, cardiovascular/cerebrovascular/thromboembolic medical history, baseline iron replete status, and stable vs incident dialysis: dialysis duration >4 months vs ≤ 4 months where appropriate.

In addition, hemoglobin change from baseline to the average level during Weeks 18-24 may be analyzed by subgroups of baseline hs-CRP (\leq ULN, vs. $>$ ULN), baseline ESA dose categories, and dialysis status.

